**Study Design:**

Patients with recent, unilateral ACL rupture or combined ACL rupture/meniscus injury, who are undergoing surgical reconstruction, will be recruited and randomized to active NMES or control (placebo) interventions, with stratification for age, sex and graft type (knee extensor autograft, knee flexor autograft or allograft). All personnel performing assessments on patients/tissue will be blinded to group assignment. A within-subject design will be used, where the injured, surgically-treated leg will be compared to the contralateral, uninjured leg. NMES or control interventions will begin shortly following injury (within 3 wks) and run till 3 wks post-surgery. Patients will be evaluated twice pre-surgery and then at 3 wks and 6 mos post-surgery. There is the possibility for an additional visit prior to Pre-Surgery Testing #1 to assure that we consent volunteers and start the NMES/control intervention prior to 3 week post-injury. We will make every attempt to limit this

**Pre-surgery testing #1** (within 3 wks of injury) will consist of clinical/patient-oriented assessments (IKDC, KOOS) and functional testing (uninjured leg only).

**Consent/Device Training Visit** will occur within 3 wks of injury to begin the NMES/control intervention if the Pre-surgery testing #1 visit cannot be scheduled within this time constraint. Volunteers will be consented and will undergo training in the use of the NMES or control intervention (detailed below).

**NMES/Control intervention** will begin within 3 wks of injury following pre-surgery testing, with patients randomized (1:1). Active NMES intervention will consist of active NMES 5 d per week, with each session lasting 60 min. For the control intervention, volunteers will receive a sham NMES device to maintain blinding and will be told that they will receive imperceptible, microcurrent stimulation for pain mitigation. In the sham device, electrical leads are disconnected so that no current can leave the NMES device.

**Pre-surgery testing #2** (~1 wk pre-surgery) will be identical to Pre-surgery #1 testing, but will include strength testing of the injured leg.

Post-surgery testing #1 (3 wks) will consist of bilateral muscle biopsies for cellular structure and function measures and bilateral thigh muscle size assessments.

Standardized rehabilitation will begin 3 wks post-surgery, with both groups undergoing the same accelerated rehabilitation program that is standard of care within our practice.

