## **SUBJECT CHARACTERISTICS, IDENTIFICATION AND RECRUITMENT**

*Subject Selection:*

A single cohort of patients will provide data to address both aims. Patients with recent, unilateral ACL rupture or combined ACL rupture/meniscus injury, who are undergoing surgical reconstruction, will be recruited and randomized to NMES or control, with stratification for age, sex and graft type (knee extensor autograft, knee flexor autograft and allograft). A within-subject design will be used (Fig 3), where the injured, surgically-treated leg will be compared to the contralateral, uninjured leg.

We chose to study patients with ACL rupture, with or without meniscus injury, as this trauma is immediately disabling, dramatically reduces muscle strength and increases the risk of further injury and developing PTOA (1-4). Although neuromuscular adaptations differ slightly between ACL and combined ACL/meniscus injury post-surgery, injury types will be distributed equally by randomization. Inclusion of both injury types provides broader generalizability of our results. We will also stratify randomization by graft type (knee extensor autograft, hamstring autograft and allograft groups) using an adaptive randomization approach to assure that groups are frequency matched for the different graft types.

Use of the uninjured leg as a within-subject control is common in this field and justified by results from our labs (4) and others (5) showing that its size and function are maintained throughout the proposed study period (4, 5). While whole muscle strength in the uninjured leg is reduced slightly compared to uninjured control volunteers due to cross-over neural inhibition (6), there is no evidence that this would affect the intrinsic structure or function of its single muscle fibers differently in NMES and control groups. Nonetheless, we will assess strength in the uninjured leg repeatedly throughout the study to verify its constancy and, in turn, its suitability as a within-subject control, particularly for the secondary aim.

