To obtain data to estimate samples sizes based on these relative differences, we used a larger data set of knee OA patients (n=16) assessed for identical measurements proposed in this application (single fiber CSA and function). Mixed linear models were developed to estimate both between cluster variances and intraclass correlation coefficients (ICC), where samples were obtained at times before and after treatment, with clusters of fibers available for each volunteer at each time point. Cluster variance and ICC estimates were 1,030,622 and 0.337 for MHC I CSA; 1,047,066 and 0.383 for MHC II CSA; 254 and 0.263 for MHC IIA tension and 576 and 0.610 for MHC IIA velocity, respectively. These data were then used in a two group repeated measures analysis of variance model to estimate power for group, leg and group X leg interaction effects. Using relative differences detailed above and variance estimates from our mixed model analyses, we estimated that an n=10/group would detect significant group X leg interaction effects for MHC I CSA and MHC IIA tension and velocity, with powers in excess of 80% (87%, 99% and 99%, respectively) at a significance level of 5%. We chose these three variables because they represent important determinants of whole muscle size and function. More specifically, as the most prevalent fiber type in muscles (3, 4), MHC I CSA is the most important factor determining whole muscle size. Similarly, given that MHC IIA fibers are the most prevalent fast-twitch, type II fiber in human muscle, it disproportionately determines the contractile characteristics of whole muscle because of its large power output (2, 5). Power output is dependent on both the force producing capacity and contractile velocity of the constituent fibers (ie, power=force X velocity). Thus, we have included both force and velocity in our sample size estimates. Of note, we did not focus on MHC IIAX fiber function because, unlike our studies in older adults, where these fiber types are much more prevalent, far fewer of these fibers are present in younger adults (4), who will comprise the majority of our ACL injured population. Assuming ~20% dropout rate, based on our prior work (6-8), we will enroll 12 individuals/group with the expectations of a final sample size of 10/group.

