In Aim 2, our primary outcome is knee extensor isokinetic torque. Using our data in ACL reconstructed patients (Fig 1), we anticipate reductions in isokinetic muscle strength at 6 months post-surgery of -30% vs. uninjured leg in volunteers randomized to the control group (10). Given the effect of NMES to prevent atrophy and contractile dysfunction at the cellular level (Fig 2) and preliminary evidence from others showing that NMES maintains whole muscle size and strength post-surgery (11), we predict that loss of isokinetic strength will be minimal at 6 months (~5% loss or 95% of uninjured) in the NMES group. Based on these differences, a sample of n=10/group would detect a group X leg interaction effect with 80% power and a significance level of 0.05. We have not performed sample size estimates on secondary outcome variables, as it is unlikely that our sample size and length of follow-up will be sufficient to detect effects of NMES on these factors. In anticipation of observing salutary effects of NMES on muscle size and function (Aim 1), analyses of these secondary outcome variables will provide preliminary data to inform power calculations for future randomized controlled clinical trials to interrogate broader clinical efficacy of NMES to mitigate skeletal muscle structural and

functional adaptations to traumatic knee injury and surgical intervention, with the goal of mitigating long-term knee pathology (10).

Statistical analytical approach: Our primary goal is to assess the effect of group assignment (NMES vs. control) on skeletal muscle fiber size and contractile function 3 wks post-surgery using a mixed model, with group and leg (injured vs. non-injured) as fixed effects and subject ID and fiber number as random effects to account for the pairing of legs and clustering of fibers within each volunteer, respectively, as generally described (21). Primary outcomes include: MHC I and II fiber CSA and MHC IIA tension (force/CSA) and velocity. Any confounding factors differing between groups (eg, physical activity level, time between injury and surgery, tourniquet time during surgery) can be included as covariates, although most factors should be balanced by randomization.

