The goal of this analysis is to determine whether dynamic muscle strength is better preserved in the injured limb in the NMES group compared to controls 6 mos post-surgery. As in Aim 1, a mixed model will be used, with group and leg effects and subject ID as a random effect. As strength in the injured leg will be compared to the contralateral, uninjured leg, we will monitor strength in the contralateral leg throughout the study (Fig 3) to use as a covariate if any group differences are found. Other covariates that may differ between groups include crutch use, compliance with rehabilitation/activity restrictions and time between injury and surgery. Secondary analysis will evaluate changes in SLH, quadriceps muscle CSA, JSW, MRI outcomes and KOOS, SF-36 and IKDC scores.

References

2. Callahan, D. M., Miller, M. S., Sweeny, A. P., Tourville, T. W., [name], J. R., Savage, P. D., Maughan, D. W., Ades, P. A., [name], B. D., and [name], M. J. (2014) Muscle disuse alters skeletal muscle contractile function at the molecular and cellular levels in older adult humans in a sex-specific manner. *J Physiol* 592, 4555-4573
3. Callahan, D. M., Tourville, T. W., Miller, M. S., Hackett, S. B., Sharma, H., Cruickshank, N. C., [name], J. R., Savage, P. D., Ades, P. A., Maughan, D. W., [name], B. D., and [name], M. J. (2015) Chronic disuse and skeletal muscle structure in older adults: sex differences and relationships to contractile function. *Am J Physiol Cell Physiol* 308, C932-C943
4. Miller, M. S., Bedrin, N. G., Callahan, D. M., Previs, M. J., Jennings, M. E., Ades, P. A., Maughan, D. W., Palmer, B. M., and [name], M. J. (2013) Age-related slowing of myosin actin cross-bridge kinetics is sex specific and predicts decrements in whole skeletal muscle performance in humans. *J Appl Physiol* 115, 1004-1014

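### Allocation is balanced on age, sex and graft type, but neither primary model uses these factors; a small pre-specified set of factor x leg terms would be a cheap improvement, mainly for Aim 2

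*SAP*

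**What the plan says.** Protocol, Study Design: patients are randomized 1:1 "with stratification for age, sex and graft type (knee extensor autograft, knee flexor autograft or allograft"). Protocol, Subject Selection, repeats the three factors and says that graft type is handled "using an adaptive randomization approach to assure that groups are frequency matched for the different graft types".

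SAP, Statistical analytical approach: the Aim 1 model is a mixed model "with group and leg (injured vs. non-injured) as fixed effects and subject ID and fiber number as random effects". For Aim 2, "a mixed model will be used, with group and leg effects and subject ID as a random effect". Age, sex and graft type appear in neither model.

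The Aim 1 covariate rule is: "Any confounding factors differing between groups (eg, physical activity level, time between injury and surgery, tourniquet time during surgery) can be included as covariates". Aim 2 has a similar list (strength of the uninjured leg, crutch use, compliance, injury-to-surgery time).

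The SAP's sample size section powers the group x leg interaction in both aims. For Aim 2, "a sample of n=10/group would detect a group X leg interaction effect with 80% power and a significance level of 0.05". The model descriptions do not write that interaction out.

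**The concern.** The sponsor judged three factors important enough to force balance on them, and the analysis then leaves them out. If such a factor predicts the outcome contrast, its variance stays in the error term although the allocation has removed most of its effect on the group comparison. The estimated standard error is then larger than the true one, and the test is conservative. The covariate rule does not repair this: it is triggered by an observed group difference, which is what balanced allocation prevents.

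The usual remedy, adding the factors as main effects, would do nothing here. The outcome contrast is injured minus uninjured leg within a patient, and anything that shifts both legs equally cancels. Only a factor that changes the leg difference matters. The clearest candidate is graft type: one category is a knee extensor autograft, and the Aim 2 endpoint is knee extensor torque. With about 20 patients analysed, precision lost here is hard to recover elsewhere.

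**Working it through.** **Step 1. The SAP's own figure.** With one torque value per leg, group x leg is a two-sample t test on D = injured minus uninjured. Inputs from the SAP: 10 per group, 5% level (two-sided assumed), control loss 30%, NMES loss 5%, so the effect is 30 - 5 = 25 points. No SD is given, so the 80% cannot be reproduced directly. With 18 df, 80% power needs a noncentrality of 2.963. Then d = 2.963 x sqrt(2/10) = 1.325, and the implied SD of D is 25/1.325 = 18.9 points. I take this as the base case. For Aim 1 the same inversion gives d = 1.46 for the stated 87% (MHC I CSA) and d = 2.03 for the stated 99% (MHC IIA tension and velocity).

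**Step 2. Which terms matter.** D for a patient equals leg + group x leg + factor x leg + error; all patient-level main effects drop out. Let R2 be the share of the variance of D, within group, that factor x leg terms explain. The documents give no value, so a range is shown.

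**Step 3. Level of the unadjusted test.** Under exact balance the estimated SE exceeds the true SE by 1/sqrt(1 - R2), which is 1.12 at R2 = 0.2 and 1.20 at 0.3. Real allocation balances less well: simulated minimisation on all three factors gives an excess of 4% and 7%. Simulated type I error of the unadjusted test:

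| Allocation assumed | R2 = 0.2 | R2 = 0.3 |
|---|---|---|
| Minimisation on three factors, grafts 40/40/20%, 24 allocated, 20 analysed | 3.3% | 3.0% |
| Minimisation on three factors, grafts 50/35/15%, 20 patients | 4.1% | 3.4% |
| Blocks of 4 in 12 strata (2 x 2 x 3) | 4.3% | - |
| Minimisation on graft only | 4.5% | - |

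**Step 4. Power for Aim 2, two terms.** Terms: knee extensor autograft versus other, and sex, each x leg. Setting: 24 minimised on three factors, 20 analysed, grafts 40/40/20%, R2 carried by extensor graft and sex, 2,500 replicates (Monte Carlo error sqrt(0.8 x 0.2/2500) = 0.8 points).

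| R2 | Unadjusted | Two terms |
|---|---|---|
| 0 | 80% | 77% |
| 0.1 | 80% | 81% |
| 0.2 | 80% | 84% |
| 0.3 | 82% | 90% |
| 0.4 | 83% | 93% |

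The adjusted type I error stays at 4.8-5.6%. The gain is 84 - 80 = 4 points at R2 = 0.2, 90 - 82 = 8 at 0.3 and 93 - 83 = 10 at 0.4. Break-even is near 0.1, or 0.1 to 0.2 if age also carries some of the variance.

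**Step 5. Power with all factors (4 df: sex 1, age 1, graft 2).** Under exact balance, power is that of a noncentral t with noncentrality 2.963/sqrt(1 - R2) and 14 df: 78.7% at R2 = 0, 82.7% at 0.1, 86.8% at 0.2 and 90.8% at 0.3. Under simulated minimisation (grafts 50/35/15%), unadjusted against adjusted is 80 v 74%, 80 v 77%, 81 v 82% and 82 v 87%. With minimisation on graft only, it is 79.7 v 71.4% at R2 = 0. The full set is expensive at this size.

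**Step 6. Aim 1 as worded.** Random effects for subject and fiber number do not include subject-by-leg. Set the total fiber variance to 1 for MHC I CSA with the SAP's ICC of 0.337, so between = 0.337 and within = 0.663. Assume 100 fibers per leg and a share s of the between variance at subject-by-leg level. The true variance of group x leg is (2/10) x 2 x (0.337s + 0.663/100).
- s = 0.05: 0.4 x (0.01685 + 0.00663) = 0.0094, SE 0.097.
- s = 0.5: 0.4 x (0.1685 + 0.00663) = 0.0701, SE 0.265.
- Model without the term: about 0.4 x 0.00663 = 0.00265, SE 0.051.

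Simulation agrees: model SE 0.052-0.054 against true 0.099-0.273, with type I error 29-71%. At 10 fibers per leg, type I error is 8-22% for tension and 13-46% for velocity. Here the error bars are too narrow.

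**The case against.** The strongest reply is that nothing planned is lost. Unadjusted power stays at 80-83% at every R2 in the Step 4 table, and the shift in type I error is conservative, so there is no false-positive harm from the omission. This stands: the cost is a gain forgone, not a shortfall against the plan.

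Second, any benefit needs the factors to explain roughly 10% or more of the leg-difference variance, and no document estimates that. This also stands. The graft argument is reasoning from which muscle is measured. Support for sex is thinner: it rests on titles of cited papers, which refer to older adults, while this trial enrols ages 18-50.

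Third, the allocation method is not fully described. Adaptive allocation is stated for graft type only. If only graft is balanced, the conservatism is smaller and the full four-term model costs about 8 points when the factors are irrelevant. This argues for a small set of terms, not for none.

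Fourth, the covariate rule does not bar these factors. True, but it is optional, depends on observed imbalance and names no leg interaction.

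A reader might infer that the error bars are too wide in both aims. The documents do not support that. For Aim 2 it is conditional on R2, and for Aim 1 as literally worded the direction is reversed.

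**Conclusion.** The omission is certain; its consequence is conditional. For Aim 2, if the allocation factors explain 20-30% of the variance of the injured-uninjured difference, the planned test runs at about 3-4.5% and forgoes up to about 10 points of power, depending on which factors carry the variance. At R2 = 0 there is no loss. It should not be read as showing that the trial is underpowered or that its comparison is biased.

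For Aim 1, conservatism can arise only after a subject-by-leg random effect is included; without it, anti-conservatism is the larger problem. Even then, tension and velocity, at a stated 99% power, have almost nothing to gain.

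Assumptions: two-sided 5%, 10 analysed per group, SD of 18.9 points implied by the stated 80%, assumed graft mixes, minimisation or blocked strata as shown, and for Aim 1 an assumed fiber count per leg and variance split. On this basis, using the allocation factors is a cheap improvement worth making, not a correction of an invalid analysis.

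**What to change.** In the SAP, Statistical analytical approach, for both aims:

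- Write out group x leg as the tested term.
- In Aim 1, add a subject-by-leg random effect.
- Pre-specify graft type (knee extensor autograft versus other, a grouping fixed in advance) and sex, each with its x leg term, using the values recorded at allocation. These enter whether or not the groups differ.
- Report as sensitivity analyses the model without these terms and a model adding age x leg.

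This is a wording change, and the data are already collected for allocation. It uses 2 df. If the factors explain nothing, the cost is about 2-3 points of power (about 1 point for the graft term alone). Break-even is near 10% of leg-difference variance, or 10-20% if age also carries some of it. These costs assume minimisation on all three factors, so the SAP should also state how age and sex are balanced.
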